The outcome measure for the current study is percent words correct (PWC). To test whether there is a difference in PWC between the experimental conditions, linear mixed effects regression analysis will be used. Each mixed effects model will control for covariates including individual age, gender, MOCA score, audiometric thresholds, frequency-specific audibility of stimuli, and QuickSIN scores. We will also assess PWC scores in quiet as both a covariate and as a potential moderator—thereby controlling for baseline perception capabilities—and intra-individual variability. Of particular interest is whether the IBM-processed speech is significantly more intelligible than unprocessed speech in noise (which would indicate that IBM processing provides benefit). These models will also test whether IBM-processed speech is not significantly different from unprocessed speech in quiet (which would provide evidence that IBM processing restores intelligibility of speech in noise to that of speech in quiet). These tests will be done systematically. The first aim includes the unadjusted (bivariate) model as well as the adjusted model discussed in the Research Strategy. Aim 2 builds on this by including important moderators.

For power, we used the *simr* R package to simulate power given the sample size and expected effect sizes. This analysis relied on Monte Carlo simulations from a known population model. All code used is provided below. For Aim 1, a minimum of 30 participants will be tested per sub-experiment, as this results in sufficient power for the planned comparisons (for alpha of .05, with 6 covariates, effect size of .5, power = .93).

For Aim 2, at least 30 participants will be tested, as the power analyses with a moderate interactive effect indicate this sample size will result in sufficient power for the planned interactions (for alpha of .05, with 6 covariates, power = .91).

The R code to run the analyses are provided below.

```
library(tidyverse)
set.seed(843)

library(simr)

data_production <- function(npart = 30,          ## number of subjects
                           nplot = 6,          ## number of repeated measures
                           effect_x = .5,      ## effect of variable x
                           sigma_s = 2,         ## variance within participant
                           sigma = 1) {         ## residual variance

  x = rep(1:nplot, times = nplot)
  z = rnorm(npart*nplot)
  a = rnorm(npart*nplot)
  b = rnorm(npart*nplot)

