  c = rnorm(npart*nplot)
  d = rnorm(npart*nplot)
  e = rnorm(npart*nplot)
  f = rnorm(npart*nplot)
  standeff = rep( rnorm(npart, 0, sigma_s), each = nplot)
  stand = as.character(rep(1:npart, each = nplot))
  ploteff = rnorm(npart*nplot, 0, sigma)
  resp = 1 + effect_x*x + standeff + ploteff
  dat = data.frame(x = as.character(x), z = scale(z), stand, resp = scale(resp), a, b, c, d, e, f)
  dat
}

data_production_int <- function(npart = 30,          ## number of subjects
                                 nplot = 6,          ## number of repeated measures
                                 effect_x = .5,      ## effect of variable x
                                 sigma_s = 2,         ## variance within participant
                                 sigma = 1) {         ## residual variance

  x = rep(1:nplot, times = nplot)
  z = rnorm(npart*nplot)
  a = rnorm(npart*nplot)
  b = rnorm(npart*nplot)
  c = rnorm(npart*nplot)
  d = rnorm(npart*nplot)
  e = rnorm(npart*nplot)
  f = rnorm(npart*nplot)
  standeff = rep( rnorm(npart, 0, sigma_s), each = nplot)
  stand = as.character(rep(1:npart, each = nplot))
  ploteff = rnorm(npart*nplot, 0, sigma)
  resp = 1 + effect_x*x + effect_x*x*z + effect_x*x*x*z + standeff + ploteff
  dat = data.frame(x = as.character(x), z = scale(z), stand, resp = scale(resp), a, b, c, d, e, f)
```

```

dat
}

d <- data_production()
fit <- lmer(resp ~ x + a + b + c + d + e + f + (1|stand), data = d)
fit2 <- extend(fit, along="stand", n=30)
fixef(fit2)[2:3] <- 0.15
fixef(fit2)[4:5] <- 0.30
fixef(fit2)[6] <- 0.45

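### The Aim 1 power of .93 roughly reproduces, but it is an apparent omnibus power in total-SD units that depends on an unsupported listener SD and one random data set, not power for an effect of .5 on the planned comparisons

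*Combined protocol and SAP*

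**What the plan says.** Under Statistical Design and Power, the plan sets the Aim 1 sample size as follows: "a minimum of 30 participants will be tested per sub-experiment". The support is a simulated power, "for alpha of .05, with 6 covariates, effect size of .5, power = .93", and the text describes its basis thus: "This analysis relied on Monte Carlo simulations from a known population model".

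The R code in the same section does this:

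- It draws a listener effect with SD `sigma_s` = 2, "standeff = rep( rnorm(npart, 0, sigma_s), each = nplot", and a residual with SD `sigma` = 1. The code comments label these a within-participant variance and a residual variance, but both are passed to `rnorm` as SDs, and the first is a between-listener SD.
- It builds the response with a slope of .5 per condition step, "resp = 1 + effect_x*x + standeff + ploteff".
- It standardises that response before output, "dat = data.frame(x = as.character(x), z = scale(z), stand, resp = scale(resp), a, b, c, d, e, f".
- It generates one data set, "d <- data_production", fits the mixed model once, and overwrites the condition coefficients: "fixef(fit2)[2:3] <- 0.15" for levels 2 and 3, then 0.30 for levels 4 and 5 and 0.45 for level 6.
- It runs `powerSim` on that fit without naming a test.

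The same section says that the comparison of most interest is IBM-processed speech against unprocessed speech in noise.

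**The concern.** All six conditions are rows within each listener, so between-listener variance cancels from every condition contrast. The code nevertheless divides the response by a total SD that contains that variance, and only then fixes the coefficients. On this scale a larger listener SD makes the residual look smaller while the coefficients stay put, so the reported power rises. The residual SD used by `powerSim` is also an estimate from a single random draw, although the text says that the population model is known.

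The quoted effect of .5 is not what is tested either. The slope of .5 is overwritten, and it survives only as a contribution to the total SD.

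At stake is the one figure that supports 30 listeners. A reader cannot convert .15 into percent-words-correct (PWC) points, and cannot tell from .93 how likely the study is to detect an IBM benefit.

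**Working it through.** **Inputs from the code:** 30 listeners, 6 conditions, listener SD 2, residual SD 1, slope .5, seed 843, imposed coefficients 0, .15, .15, .30, .30, .45, six covariates, alpha .05. **Assumption:** the default test is the 5-df test of condition. The documents do not name the test. The simr package was not available, so power was computed from the non-central F distribution and checked by direct simulation.

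**1. The plan's own figure.** The seed-843 data set was regenerated and the random-intercept model refitted. The sample total SD is 2.285, the scaled residual SD 0.408 and the scaled listener SD 0.888. With the imposed coefficients and the six covariates, the noncentrality is 20.2. With 180 − 30 − 5 − 6 = 139 denominator df, power is .946 by F (simulated .945) and .954 by chi-square. The stated .93 is within 2 points of the F result.

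**2. What the rescaling does.** Expected total variance = listener SD² + residual SD² + .5² × Var(x), where Var(x) for 1 to 6 is 35/12.

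- At the code's inputs: 4 + 1 + 0.73 = 5.73, so the total SD is 2.394. Between-listener variance is 4/5.73, about 70% of it.
- The scaled residual SD is 1/2.394 = 0.418.

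The noncentrality, ignoring the covariates, is 30 × Σ(b − mean b)² / (scaled residual variance). The mean coefficient is 0.225 and the sum of squares is 2 × 0.050625 + 4 × 0.005625 = 0.12375, so the numerator is 3.7125. With residual SD 1, dividing by 1/(total variance) is the same as multiplying by the total variance:

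| Listener SD | Total variance | Scaled residual SD | Noncentrality | Power, F(5,139) | Raw size of the .15 coefficient |
|---|---|---|---|---|---|
| 0.5 | 1.98 | 0.711 | 7.3 | .50 | 0.21 |
| 1 | 2.73 | 0.605 | 10.1 | .66 | 0.25 |
| 1.41 | 3.73 | 0.518 | 13.8 | .82 | 0.29 |
| 2 | 5.73 | 0.418 | 21.3 | .96 | 0.36 |

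The last column shows why power moves: the raw effect implied by a fixed coefficient grows with the listener SD.

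**3. Isolating the cause.** Leave the response unscaled, with residual SD 1, and hold the raw effects at 0.36, 0.72 and 1.08 (.15, .30 and .45 × 2.394). Power is then about .95 at listener SD 0.5, 1, 2 and 3 alike. The dependence on listener SD comes from the rescaling combined with the fixed coefficients.

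**4. Dependence on the single draw.** Repeating the code's own inputs over 2,000 seeds, with the covariates in the model, gives a median F power of .94 and a central 95% range of .78 to .99. Leaving the covariates out gives .81 to .995.

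**5. Single contrasts at the code's inputs.** The standard error against level 1 is about 0.408 × √(2/30) = 0.105. The ratios are .15/0.105 = 1.4, .30/0.105 = 2.9 and .45/0.105 = 4.3. With the six covariates in the seed-843 fit, power is about .28 to .29, .78 to .79 and .985.

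**The case against.** The strongest reply is that nothing was miscalculated. This stands: .93 is a typical value under the declared inputs, the seed is disclosed, and more than 95% of generated data sets give power above .80.

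A second reply is that effects in total-SD units are a legitimate convention. If effects are defined that way, power should rise with the listener SD, because the raw effect rises too. This also stands, so the table in step 2 shows sensitivity to an input, not an error. But the plan gives no reason for choosing that scale or for a listener SD twice the residual SD, and it reports the result as power for an effect of .5.

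Third, `powerSim` does simulate from fixed values, so the text's description of its basis is loose and not false. That is fair. The variance values are still estimates from one draw, although the generating values of 2 and 1 could have been supplied directly.

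Three stronger readings are tempting, and the documents do not support them:

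- **That true power is about .26.** This follows only if .15, .30 and .45 are taken in residual-SD units, which the plan does not say.
- **That power is .50 or .66.** These need listener SDs of 0.5 or 1, which the plan does not use. No PWC variance is given that would make them more plausible than 2.
- **That 30 listeners are too few.** This would need a PWC residual SD and a target difference for IBM versus noise, and neither is given. Nor does the code say which levels stand for noise and for IBM, so the single-contrast figures cannot be read as the power for that comparison.

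**Conclusion.** The point holds as a criticism of what .93 represents, not of its arithmetic. The figure reproduces to within about 2 points. It describes an omnibus test, if the default is the 5-df test of condition, with effects expressed in a total SD that is about 70% listener variance by assumption, and with variance components from one random data set. It is not the power for an effect of .5 on the planned comparisons.

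In size: with residual SD 1 and the coefficients unchanged, power runs from about .50 to .96 as the listener SD goes from 0.5 to 2. At the code's own inputs it varies with the draw over a central 95% range whose lower end is .78 to .81, depending on whether the covariates are fitted, and whose upper end is about .99. A single contrast of .15 or .30 against level 1 has power of about .28 or .79, well below .93.

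The `scale(resp)` step also appears in the Aim 2 data function. The Aim 2 figure was not recomputed here.

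**What to change.** 1. Remove `scale(resp)` and state the assumed condition differences in PWC points, labelling each level by its condition.
2. Set the listener SD and residual SD explicitly on the PWC scale, for example with `makeLmer` and fixed `VarCorr` and `sigma`, and give their source. Correct the code comments that call these inputs variances.
3. Replace .93 with the power for the IBM-versus-noise contrast, naming the test, over a stated range of residual SD and with the Monte Carlo interval. If an omnibus power is kept, label it as such and delete the reference to an effect size of .5.

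Removing the rescaling alone will not change the figure if the raw effects are kept equivalent (about .95). The gain comes from interpretable effects, justified SDs and the right contrast.

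The cost is about an hour of re-coding and a restated figure that may be less favourable. Any consequence for the sample size cannot be judged until the PWC SDs are supplied.

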# summary(fit2)

broom:::augment(fit2) %>%
  ggplot(aes(factor(x), .fitted, fill = factor(x), color = factor(x))) +
  geom_boxplot(alpha = .7) +
  theme_classic() +
  scale_fill_viridis_d() +
  scale_color_viridis_d() +
  theme(legend.position = "none")

sim1 <- powerSim(fit2)
sim1

d2 <- data_production_int()
fit <- lmer(resp ~ x*z + a + b + c + d + e + f + (1|stand), data = d2)
fit2 <- extend(fit, along="stand", n=30)
fixef(fit2)[14] <- 0.2
fixef(fit2)[15] <- 0.2
fixef(fit2)[16] <- 0.3
fixef(fit2)[17] <- 0.3
fixef(fit2)[18] <- 0.4

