All participants will be seated in a sound treated booth and fitted with *Sennheiser HD280 Pro* circumaural headphones. Hearing-impaired participants will not wear their hearing aids during testing, but audibility will be ensured through the spectral shaping via a digital equalizer. Participants will be told that they will be presented with phrases that will be difficult to understand, either because the phrases will be produced by a person with a speech disorder and/or background noise, and that their job is to listen carefully and try to understand what is being said. The experimenter will present the phrases, one at a time, and following each phrase, the participants will be asked to repeat back what they think they heard. The experimenter will type out the participant's verbal responses. This method was selected over more traditional "hear and type" methods to mitigate possible issues with mobility and typing competencies, particularly applicable to the older listeners. Responses will be scored for words correct, using previously established scoring criteria for the semantically anomalous phrases and a validated in-house computer program.

Multiple regression analysis will be used to test for differences in PWC scores across the conditions. Each model will control for individual age, gender, and PWC scores in quiet—thereby controlling for baseline perception capabilities.

Statistical Design and Power

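### In the coded Aim 2 model, main-effect covariates do not adjust the condition-by-moderator test, so a correlated trait's moderation of IBM benefit can be credited to the tested moderator

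*Combined protocol and SAP*

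**What the plan says.** The Study Protocol section shows a mixed listener sample. It states that "Hearing-impaired participants will not wear their hearing aids during testing", and it justifies the spoken-response method as "particularly applicable to the older listeners". The supplied text gives no rule that matches, stratifies or restricts age by hearing status.

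The Statistical Design and Power section sets out the adjustment: "Each mixed effects model will control for covariates including individual age, gender, MOCA score, audiometric thresholds, frequency-specific audibility of stimuli, and QuickSIN scores". Quiet scores have a double role: "We will also assess PWC scores in quiet as both a covariate and as a potential moderator". For the second aim the prose says only "Aim 2 builds on this by including important moderators". It does not name those moderators, apart from quiet PWC, or say whether they are fitted together.

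The one Aim 2 model given in full is in the R code that closes the section: "fit <- lmer(resp ~ x*z + a + b + c + d + e + f + (1|stand), data = d2"). Condition (x) interacts with one generic moderator (z). The six unlabelled covariates, a to f, have main effects only. The code is introduced with "The R code to run the analyses are provided below", although what it runs is a power simulation.

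**The concern.** A reader of the prose would take the Aim 2 interaction tests to be adjusted for age and hearing. In the coded model they are not. Adding age as a main effect moves all six of a listener's scores by the same amount. It says nothing about whether older listeners gain more or less from IBM. If they do, and the tested moderator (quiet PWC, for example) goes with age, the moderator picks up part of that effect even though age is in the model.

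At stake is what Aim 2 may conclude. The protocol says the study will inform a proposal for a large-scale evaluation. A trait named there as a driver of IBM benefit might only be standing in for age or hearing.

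The power simulation cannot reveal this. It draws z and a to f as independent noise, new on every row, whereas most of the real traits are fixed per listener and may be correlated.

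**Working it through.** **The plan's own figures.** Rebuilding the posted code as a simulate-and-refit loop with likelihood-ratio tests gives Aim 1 power of about 0.95 (stated .93). For Aim 2 it gives 1.00 on every generated data set, so the stated .91 is not reproduced. That is a separate matter: the generating formula shrinks the scaled residual SD to about 0.07-0.10, and the coded comparison also drops the six covariates.

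**Why the main effect does not adjust.** For listener i in condition j, write

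y_ij = m_j + g·a_i + d_j·z_i + u_i + e_ij,

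with a_i a covariate fixed per listener. Subtracting noise from IBM gives

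y_i,IBM − y_i,noise = (m_IBM − m_noise) + (d_IBM − d_noise)·z_i + error.

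The term g·a_i is gone. If the truth is that a_i changes IBM benefit with slope b and z_i does not, and both are standardised with correlation r, the fitted slope on z_i has expectation r·b.

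**Inputs.**
- 30 listeners and six conditions: Statistical Design and Power.
- Residual SD on the scaled response: the Aim 1 generator implies 1/√(4 + 1 + 0.25 × 35/12) = 1/√5.73 = 0.42; 0.43 is used.
- Slope b = 0.2 or 0.3 in the two IBM conditions only: assumed. The code's own interaction coefficients run from 0.2 to 0.4.
- r = 0, 0.3, 0.5, 0.7: assumed; no figure is in the documents.

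**IBM-versus-noise slope by formula.** Take the mean of the two IBM conditions minus the mean of the two noise conditions. Its residual SD is 0.43 × √(4 × 1/4) = 0.43, plus the unexplained part of the omitted trait:

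SE = √(0.43² + b²(1 − r²)) / √29.

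- r = 0.5, b = 0.2: false slope 0.10; SE = √(0.1849 + 0.0300)/5.385 = 0.086; ratio 1.16; rejection about 20%.
- r = 0.5, b = 0.3: false slope 0.15; SE = √(0.1849 + 0.0675)/5.385 = 0.093; ratio 1.61; rejection about 34%.

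**Simulated rejection rates for a moderator with no independent effect (b = 0.2 to 0.3).**

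| r | 5-df condition-by-moderator test | IBM-versus-noise slope |
|---|---|---|
| 0 | 5% | 5% |
| 0.3 | 9-14% | 10-15% |
| 0.5 | 16-30% | 20-34% |
| 0.7 | 28-54% | 36-61% |

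Repeat runs agree to within about 3 percentage points. With the interaction of the omitted trait added, the rates return to about 5%.

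**Roles reversed.** Let hearing be the only true moderator, with the code's coefficients 0.2, 0.2, 0.3, 0.3, 0.4, residual SD 0.41 and intercept SD 0.88. The condition-by-age test is then significant in 7%, 15%, 30% and 55% of trials at r = 0, 0.3, 0.5 and 0.7. Adding condition by hearing brings it to 8% throughout (the likelihood-ratio test is slightly liberal at this size).

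**Precision cost.** With one added correlated trait, the SE rises by 1/√(1 − r²): 1/√0.75 = 1.15 at 0.5 and 1/√0.51 = 1.40 at 0.7. If two added traits and the moderator all correlate equally, R² = 2r²/(1 + r). At 0.5 this is 0.333, factor 1.22; at 0.7 it is 0.576, factor 1.54. In the reversed-role simulation, 5-df power for the true moderator falls from 0.91 fitted alone to 0.80 and 0.62 with both interactions fitted.

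**The case against.** The strongest objection is that the quoted line belongs to power code with unlabelled noise variables, and that the analysis plan is the prose. The prose speaks of moderators in the plural, so joint fitting is not excluded. It also points to an adjusted model in a Research Strategy that is not among these documents. This stands in part: the code does not prove how the real data will be analysed. But the plan presents it as the analysis code, and nothing in the supplied text mentions a condition-by-covariate term.

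Three further points stand and limit the claim:
- Without correlation there is no leak, and the documents neither report one nor show that an omitted trait moderates benefit.
- An unadjusted moderator slope correctly answers whether a measure predicts who benefits. The rates above are false positives only for the question of an independent effect, and the documents do not say which question Aim 2 asks.
- Frequency-specific audibility could vary by condition, in which case its main effect does not cancel. The argument covers traits fixed per listener.

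A reader might infer that Aim 2 will in fact misattribute moderation, or that the planned covariate control is absent altogether. The documents support neither. They name neither age nor hearing as a moderator, and main effects still adjust overall score levels.

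**Conclusion.** The point holds as a conditional one. As coded, the Aim 2 interaction test is not adjusted for listener-level covariates, despite the stated control. That part is algebra and needs no assumption beyond traits fixed per listener. The size of the consequence rests wholly on the assumed correlation and the assumed slope of the omitted trait. It runs from none at zero correlation to more than half of trials at 0.7 with the larger slope. The simulations use a generic moderator. They do not carry over directly to quiet PWC, which is also the outcome in conditions 1 and 2 and so is tied to the response by construction. The finding warrants a limit on what Aim 2 may claim, with a second reported model. It does not warrant replacing the coded model.

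**What to change.** Name the Aim 2 moderators and keep the coded model. For each moderator, including quiet PWC, also report its IBM-versus-noise slope from a model with two added terms: IBM-versus-noise by age, and IBM-versus-noise by one summary hearing measure fixed in advance (for example mean audiometric threshold). Omit whichever of these is the moderator under test.

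Describe a moderator as independent of age and hearing only if it holds in the adjusted model. Otherwise state that it predicts benefit but cannot be separated from age or hearing in this sample.

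The cost is a sentence of plan text and at most two parameters, using covariates already planned. The adjusted slope loses precision as shown above, and the power figures there are only indicative because they come from a 5-df test with full interactions. A non-significant adjusted slope is therefore not evidence of no moderation. If quiet PWC or QuickSIN partly reflects hearing, the adjustment may remove some of its real effect, which is why both models should be shown. The change does not resolve the overlap between quiet PWC and the outcome, which needs its own treatment.

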# summary(fit2)

broom:::augment(fit2) %>%
  ggplot(aes(z, .fitted, fill = factor(x), color = factor(x))) +
  geom_point(alpha = .7) +
  geom_smooth(method = "lm") +
  theme_classic() +
  scale_fill_viridis_d() +
  scale_color_viridis_d()

sim2 <- powerSim(fit2, test = fcompare(~ x + z))
sim2

```

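### The Aim 2 power code drops the six covariates along with the interaction, so it does not test the interactions for which power of .91 is reported

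*Combined protocol and SAP*

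**What the plan says.** The Statistical Design and Power section sets the Aim 2 size ("For Aim 2, at least 30 participants will be tested") and justifies it by saying that "this sample size will result in sufficient power for the planned interactions (for alpha of .05, with 6 covariates, power = .91"). It describes the figures as simulated with the simr package and adds that "All code used is provided below".

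In the R code, the full Aim 2 model is "fit <- lmer(resp ~ x*z + a + b + c + d + e + f + (1|stand), data = d2"). Here `x` is condition, `z` the moderator, `a` to `f` the six covariates and `stand` the listener. The power calculation is the last step: "sim2 <- powerSim(fit2, test = fcompare(~ x + z")). The same section says that every mixed model will adjust for covariates, and names six: age, gender, MOCA, audiometric thresholds, audibility and QuickSIN.

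**The concern.** A test of moderation should compare two models that differ only in the condition-by-moderator terms. The printed comparison model also leaves out `a` to `f`. Its null hypothesis is therefore that there is no interaction and no covariate effect, and anything the covariates explain counts towards rejection. The text presents the result as power for the interactions with six covariates, but those covariates sit only in the larger model.

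The .91 is the only stated support for 30 participants in Aim 2, and moderation is what Aim 2 adds to Aim 1. No other Aim 2 test is written out in the document.

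**Working it through.** **Inputs from the document.** Six conditions; 30 listeners; alpha .05; stated power .91. The random-intercept SD is 2 and the residual SD is 1 before the response is scaled to SD 1. Interaction coefficients (positions 14 to 18) are set to .2, .2, .3, .3, .4. The covariates `a` to `f` are random noise that does not enter the generated response, and their fitted coefficients are left as estimated.

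**Assumption.** `fcompare` takes the printed formula as the whole fixed part of the null model and keeps the listener random term.

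**Term count.**
- Full model: 1 intercept + 5 condition + 1 moderator + 6 covariates + 5 interactions = 18.
- Printed null `~ x + z`: 1 + 5 + 1 = 7. Difference: 18 - 7 = 11.
- Null with the covariates kept: 7 + 6 = 13. Difference: 18 - 13 = 5, the interactions alone.

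**Emulation.** The printed R code was re-implemented in Python: generate the data, scale the response, fit the random-intercept model, overwrite coefficients 14 to 18, simulate, and run a likelihood-ratio test at .05. Each Aim 2 scenario used 25 generated datasets with 600 simulations each.

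**Calibration on Aim 1.** Testing the five condition terms with the covariates in both models gave .957 on the seed-843 data, against the stated .93. Over 20 other datasets the mean was .944 (range .86 to .996). The emulation is therefore close to the plan's Aim 1 figure.

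**Aim 2 as printed.** Power was 1.00 in all 25 datasets on 11 df, and 1.00 in all 25 on 5 df. The stated .91 is not reproduced under either null. The reason is scale: the Aim 2 generator gives a response SD of about 11.8, so after scaling the residual SD is about 1/11.8 = 0.085 (fitted mean 0.086). The smallest planted slope is then 0.2/0.086 = 2.3 residual SDs.

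**Do the two tests address the same hypothesis?** All interaction coefficients were set to zero on the printed scale.

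| Covariate coefficients | 11-df test rejects | 5-df test rejects |
|---|---|---|
| As fitted (chance values) | 31% (11% to 88% by dataset) | 8% |
| Set to zero | 8% | 8% |

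The excess over 8% comes entirely from the covariates. The 8% itself, against a nominal 5%, is small-sample behaviour of the likelihood-ratio test and is common to both.

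**Sensitivity to scale.** The Aim 1 generator was used instead (response SD about 2.4, residual SD about 0.42), with the printed slopes.

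| Covariate coefficients | 11-df power | 5-df power |
|---|---|---|
| As fitted | .84 (.68 to .99) | .79 (.52 to .97) |
| Set to zero | .66 | .78 |

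The coded test overstates interaction power in the first row and understates it in the second.

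**The case against.** The best defence is that this is a slip in one line of a planning simulation for a proof-of-concept study, and that it changes nothing visible: with the printed inputs, power is about 1.00 under either null. That stands. It also stands that 30 is a minimum, and that nothing here shows 30 listeners to be too few. The 31% figure comes from setting the interactions to zero, which the plan never does, and from chance coefficients on noise covariates. It varies widely between datasets, so it shows that the two hypotheses differ and says nothing about whether the sample size is wrong.

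Two stronger readings are tempting, and the documents support neither.

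- A reader might infer that .91 is the power of the 11-term test. The printed 11-term test gives about 1.00, so .91 cannot be traced to this line. Its failure to reproduce is a separate problem that correcting the null model alone will not solve.
- A reader might infer that the study analysis will report ordinary effects of age or hearing as moderation. That requires the same comparison to be run on study data. The sentence "The R code to run the analyses are provided below" directly follows the two power paragraphs, and the code beneath it only simulates data and computes power. The text commits every mixed model to covariate adjustment, which argues against a null model without covariates. Any false-rejection rate would also need an assumed share of variance explained by the covariates, which the documents do not give.

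The objection does not reach the mismatch itself. The covariates are missing from the printed null model, nothing elsewhere in the document corrects this, and nothing says they were meant to be tested jointly with the interaction.

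**Conclusion.** The point holds as a mismatch between the stated hypothesis and the coded one. The Aim 2 power line tests 11 terms jointly, five interactions and six covariates, while the text reports power for the interactions. This follows from counting terms and rests only on the assumption about how `fcompare` reads its formula.

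The size and direction of the effect on power are not determined. There is no visible change with the printed inputs, and on a larger residual scale the error can go either way. The .91 is therefore a figure whose accompanying code neither tests the stated hypothesis nor reproduces the number. It should be corrected before anyone relies on it, but it is not evidence that Aim 2 is underpowered.

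**What to change.** Change the comparison to `fcompare(~ x + z + a + b + c + d + e + f)`, so that only the condition-by-moderator terms are dropped. Rerun with the effect sizes and residual scale actually intended, since the printed ones give power near 1.00, and replace .91 with the result. Add a sentence to the Aim 2 text saying that each moderator is tested by comparing models with and without the condition-by-moderator terms, with the same covariates in both.

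The cost is one line of code, one rerun, one restated figure and one sentence. The restated power may be higher or lower than .91. If it is clearly lower, the minimum of 30 for Aim 2 would need to be looked at again.
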